Conclusion of study: Formal data collection will be completed at 24 months post implantation. However, it is expected that patients will be followed for life in our clinic, as is the case for most patients implanted with DBS devices. At the end of the clinical trial, in consultation with patients' regular pain management teams, patients may be offered a potential therapeutic stimulation strategy (either open-loop or closed-loop), dependent on his or her pain alleviation from the clinical trial period. Patients will have the option to 1) continue active stimulation at the current setting with current device implantation, 2) continue stimulation but searching for a new setting, 3) discontinue stimulation (turning the device off) or 4) have the device removed. If patients opt to continue at-home active DBS after formal data collection has been completed, follow-up appointments will occur every 6 weeks.

Patient activation of the brain recording function: All data collection in the formal study visits described above will be initiated by the study staff. In addition to these data collections, the patient will be given the Intercept Patient Programmer, model 37441, allowing triggered brain data recording in their own home at specified times (see above). Patient will be instructed how to collect and download data at home. If the patient is not comfortable downloading the data at home, a family member or friend can also be taught how to use the device for download, or with the patient's permission, arrangements can be made for the study staff to visit the patient's home for data downloads. Study staff may also arrange with patients to visit their homes to help with initiating data collection. Such visits will ensure that data collection is initiated correctly, and by completing downloading at home, will reduce time spent during formal study visits to the clinic. The intercept patient programmer does not enable stimulation of the electrodes; it only enables recordings of the data and is thus safe for patients to use at-home after initial training with research staff.

Nexus System Study: Patients who have had the Activa PC+S device implanted for approximately 4 months (Phase 1 of the clinical study) will start Phase 2 of the study, which implements the Nexus external interface. The Nexus System is capable of open-loop and closed-loop stimulation, allowing potential therapeutic applications of Activa PC+S. Patients will participate in phase 2 of the trial between 7 and 12 months post implantation, involving up to ten additional study visits.

Stimulation will test a strategy of disruption of pain states, with optimal stimulation parameters to the orbital frontal and cingulate as determined by phase 1. Furthermore, closed-loop stimulation will test a strategy for automated control of DBS settings with aberrant signaling in pain states triggering stimulation. To test stimulation strategies, at the start of a session in phase 2, LFP data will be collected in elevated pain states. These data will be streamed using the Nexus System in conjunction with software from the Nexus programming interface. The Nexus System provides a conduit between Activa PC+S and a computer and can transfer stimulation update commands to Activa PC+S. During the streaming procedure stimulation settings may be automatically, iteratively, adjusted based on markers of oscillatory activity such as cortical phase-amplitude coupling (PAC) or beta band power. These adjustments will always remain within allowable settings pre-programmed by a clinician using standard procedures (i.e. using the Medtronic 8840 programmer).

Phase 2 will test the effectiveness of closed-loop stimulation in comparison to no-stimulation. Daily visits will take place for the first 2 weeks of phase 2, and regular clinic visits occurring every three weeks during Phase 2 (~ 6 months in duration).

In phase 3 (year 2 of the study), the effectiveness of closed-loop stimulation will be tested in comparison to open-loop stimulation settings. Patients will be blinded to the stimulation strategy in which they are assigned. Assignment of open-loop or closed-loop will be randomized and occur in 6-week time periods, with each patient serving as his or her control as to which stimulation treatment is more effective.

During this phase, patients will be monitored closely, with frequent at-home phone calls and in-clinic appointments. This phase of the study will last approximately 1 year (time line based on previous published reports [2, 85, 94], with in-clinic appointments occurring approximately every 6 weeks.

For the first two weeks of Phase 3, medical staff or researchers will contact patients on a daily basis to examine any changes in mood or pain symptoms. Clinic visits will also be scheduled every 6 weeks for 1 year, to examine pain and mood symptoms and routine follow-up care.

Conclusion of study: Formal data collection will be completed at 24 months post implantation. However, it is expected that patients will be followed for life in our clinic, as is the case for most patients implanted with DBS devices. At the end of the clinical trial, in consultation with patients' regular pain management teams, patients may be offered a potential therapeutic stimulation strategy (either open-loop or closed-loop), dependent on his or her pain alleviation from the clinical trial period. Patients will have the option to 1) continue active stimulation at the current setting with current device implantation, 2) continue stimulation but searching for a new setting, 3) discontinue stimulation (turning the device off) or 4) have the device removed. If patients opt to continue at-home active DBS after formal data collection has been completed, follow-up appointments will occur every 6 weeks.

The end of battery life for Activa PC+S is expected to occur 2-4 years after placement, depending on the chronic therapeutic stimulation parameters (similar to the sister device Activa PC that does not have a sensing function). The lead extender connecting the DBS leads to the pulse generator should not require replacement. When battery end of life occurs, it is expected that the Activa PC+S system will be removed, via the original chest incision, or replaced, dependent on further obtained approval based on the data collected in the present study and consultation with the regular pain management team.

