Study Design	
This is a single-center study of the effectiveness of open- and closed-loop DBS paradigms in the treatment of chronic neuropathic pain disorders that are refractory to current treatment options (e.g. two or more pain medications from different classes, spinal injections).
 
Our primary objectives are to:
 
 1) Determine the neural correlates of increased pain states in patients with chronic pain in order to enable targeted DBS treatment 2) Provide pain relief with neural stimulation 3) Establish the efficacy of open-loop and closed-loop DBS paradigms. 
DBS electrodes will be inserted into regions of the brain related to pain processing. After implantation of electrodes, study patients will undergo three phases of assessment.
 
In phase 1, patients will undergo ambulatory monitoring (~6 months) of their pain states linked to recordings of local field potentials (LFPs) in pain-processing regions. Stimulation will not be enabled during this period. This phase will be conducted in both the outpatient office setting and the patient's home environment. Throughout this period, data will be analyzed to develop a predictive model of increased pain states and to guide precision DBS treatment.
 
In phase 2, we will determine the stimulation parameters that optimally reduce the level of pain for each patient, in clinic daily, for 1-2 weeks. We will then randomly assign patients to 3-week periods of stimulation ON / stimulation OFF. We anticipate this phase will last approximately 6 months and that stimulation will be conducted in the office as well as the home setting. Patients will be under close monitoring, with frequent in-clinic appointments.

	
In phase 3, we will determine differences in pain relief efficacy for at-home open-loop versus closed-loop stimulation parameters (single-blind study). Patients will be under close monitoring, with frequent in-clinic appointments.
 
In phase 1, if data of sufficiently high quality is collected before the 6 month phase period ends, and a predictive biomarker is found before the 6-month phase period ends, the patient can accelerate to the next phases of the study to help ensure a rapid positive clinical outcome. Similarly, the patient may accelerate from phase 2 to phase 3 before the 6-month period ends to ensure rapid positive clinical outcomes.

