3.0 Study Procedure

Study Duration: The duration of this pilot study will be five years. We expect that all 10 patients will be recruited in the first 2.5 years, and data collection, stimulation and analysis will be completed at 5 years.

Patient recruitment and clinical characterization: Patients with refractory chronic neuropathic pain specific to spinal cord injury, post-stroke or phantom limb pain will be recruited from clinics specializing in chronic pain at UCSF and the San Francisco VA Medical Center. To the extent possible within our patient population, we will seek to minimize the diversity of neuropathic pain diagnoses represented across the two pain etiologies thereby optimizing opportunity for cross-patient comparative analysis.

The overall study design is summarized in **Figure 3: Overall study visit timeline. Also see Table: Protocol chart.**

The schedule of events is as follows:

PHASE 1:

Prior to surgery

1. Prior to the start of the study, an informal phone interview to schedule in-clinic evaluation will take place, **(noted as visit 1.1)**. An in-person visit at the clinic will then be scheduled.

2. The research study PI(s) will obtain informed consent at the in-person visit at the clinic. During this visit, **(noted as visit 1.2)** the study team will begin establishing eligibility based on the following inclusion and exclusion criteria, **with method for establishing eligibility in parenthesis.**

i. During this visit, PI will obtain consent for medical record review by HIPAA authorization form signed by patient. Medical record review will be also done after the in-person visit.

ii. Pregnancy test and other paper-pen testing as noted below will also be conducted.

This visit will primarily serve to obtain consent for the study and HIPAA authorization, as well as discuss the study in detail and answer any questions and begin confirmation of inclusion/exclusion criteria of the patient.

iii. During visit 1.2, Inclusion / Exclusion criteria will be investigated as follows:

Inclusion:

- Patient is age ≥ 21 years **(medical record review and asking patient);**
- Clinical diagnosis of post-stroke pain (thalamic pain), Spinal Cord Injury or phantom limb pain with allodynia or dysesthesia with pinprick anesthesia or hypoesthesia on the affected hemibody or limb (anesthesia dolorosa), **(medical record review);**

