In the first two weeks of Phase 2, patients will be seen daily for up to two weeks to optimize DBS parameters (visits 11-24), based on biomarker discovery from Phase 1. Patients will then have closed-loop stimulation enabled for at-home stimulation, with follow-up clinic visits scheduled every 3 weeks. During this phase, patients will be monitored closely, with daily at-home phone calls and frequent in-clinic appointments. Stimulation will be enabled or disabled in an ON/OFF state with patient blinded to stimulation status to test for potential placebo / sham effects. In addition to at-home reporting (similar to Phase 1), efficacy of stimulation will be tested every three weeks in-clinic. Phase 2 will last approximately 6 months in duration, time period based on previous unpublished observations in human Parkinson's patients from our group [55] and published non-human primate observations [49], visits 11-31, if needed).

Nexus System Study: Patients who have had the Activa PC+S device implanted for approximately 4 months (Phase 1 of the clinical study) will start Phase 2 of the study, which implements the Nexus external interface. The Nexus System is capable of open-loop and closed-loop stimulation, allowing potential therapeutic applications of Activa PC+S. Patients will participate in phase 2 of the trial between 7 and 12 months post implantation, involving up to ten additional study visits, in addition to daily visits for up to the first 2 weeks of phase 2.

Stimulation will test a strategy of disruption of pain states, with optimal stimulation parameters to the orbital frontal and cingulate as determined by phase 1. Furthermore, closed-

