loop stimulation will test a strategy for automated control of DBS settings with aberrant signaling in pain states triggering stimulation. To test stimulation strategies, at the start of a session in phase 2, LFP data will be collected in elevated pain states. These data will be streamed using the Nexus System in conjunction with software from the Nexus programming interface. The Nexus System provides a conduit between Activa PC+S and a computer and can transfer stimulation update commands to Activa PC+S. During the streaming procedure stimulation settings may be automatically, iteratively, adjusted based on markers of oscillatory activity such as cortical phase-amplitude coupling (PAC) or beta band power. These adjustments will always remain within allowable settings pre-programmed by a clinician using standard procedures (i.e. using the Medtronic 8840 programmer).

Phase 2 will test the effectiveness of closed-loop stimulation in comparison to no-stimulation. Daily visits will take place for the first 2 weeks of phase 2, and regular clinic visits occurring every three weeks during Phase 2 (~ 6 months in duration).

Stimulation states for Activa PC+S brain data collection: In phase 1, the optimal times of day that patients are most likely in a pain state will be assessed and used to schedule appointments in the outpatient clinic for phase 2 (i.e., we will schedule phase 2 recording and stimulation sessions for each patient to coincide with optimal time of pain states, as determined by patterns of maximum and predictable pain states from phase 1). In Phase 2, for the first recording session that includes a DBS-on condition, (after the initial up to 2 week period of optimizing stimulation parameters), the following data will be recorded:

- 1) VAS pain, VAS unpleasantness, C-SSRS, BDI/BAI, Neuropathic Pain Questionnaire, NIH PROMIS Global health and physical function scales and SF-36
- 2) Baseline LFP
- 3) Stimulation off + QST (no pain medication)
- 4) Stimulation on + QST
- 5) Wash-out, stimulation off period
- 6) LFP recording after painful activity
- 7) Recording after pain medication
- 8) EEG activity

Visits are as follows:

13. Visit 11-24: Every day for 2 weeks, stimulation optimizing:

- Clinical only: Daily visits 11-24 DBS programming initial and revisits if needed. Full history and physical exams to document changes that occur during closed loop stimulation.
- Research: C-SSRS, BDI/BAI visits 11, 18 and 24.

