3	Post-operatively, prior to hospital discharge, and during hospitalization	Clinical: follow-up physical prior to discharge Research: Activa Data collection daily, pain assessment daily for clinical characterization, and C-SSRS/BDI/BAI/ NIH PROMIS /NPQ prior to discharge	
4	10 days post implantation (+/- 3 days)	Clinical: follow up physical and staple removal and wound check Research: Teach at-home monitoring, Activa Data collection and C-SSRS/BDI/BAI/ NIH PROMIS /NPQ, (including QST+ baseline LFP recording), recording with painful activity, pain medication	
5	Three weeks post implantation (+/- 7 days) Visit for research only	Clinical: none Research visit only: visit 5 Activa Data collection and C-SSRS/BDI/BAI/ NIH PROMIS /NPQ/SF-36, (including QST), recording with painful activity, pain medication	
6	Two Months (+/- 10 days)	Clinical: HEAD CT for stability Research: Activa Data collection and C-SSRS/BDI/BAI/ NIH PROMIS /NPQ/SF-36, (including QST+baseline LFP recording), recording with painful activity, pain medication	
7	Three Months (+/- 10 days);	Clinical: none Research visit only: Activa Data collection and C-SSRS/BDI/BAI/ NIH PROMIS /NPQ/SF-36, (including QST+baseline LFP recording), recording with painful activity, pain medication	
8-10	Every 4 weeks	Clinical: visits 8 and 10: History and Physical at 4 month and 6 mo. Research: visits 8, 9, 10: Activa Data collection and C-SSRS/BDI/BAI/ NIH PROMIS /NPQ, SF-36 (including QST+baseline LFP recording), recording with painful activity, pain medication	
11-24	Every day for 2 weeks, stimulation optimizing (START PHASE 2)	Clinical only: visits 11-24 DBS programming initial and revisits if needed.; Research: 11 and 24 visit: C-SSRS/BDI/BAI	Phase 2: Months 7-12; Daily visits for 2 weeks followed by 7 study visits
25-31	every 3 weeks for closed loop randomization	Clinical: visit 28 only; History and Physical for stability Research: visits 25-31; Activa Data collection and VAS scores before and during stimulation, including QST+baseline LFP recording, recording with painful activity, pain medication. C-SSRS/BDI/BAI/ NIH PROMIS /NPQ, SF-36. DBS on/ off	

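### The Protocol Chart drops the visit-18 C-SSRS/BDI/BAI check that the procedure text requires during stimulation optimization, and both fix the last check at visit 24, which may never be held

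*Combined protocol and SAP*

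**What the plan says.** Three places in the combined protocol and SAP govern suicidality and mood scales during the first block of Phase 2.

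- **Section 3.0, numbered text for visits 11-24:** "C-SSRS, BDI/BAI visits 11, 18 and 24".
- **Section 3.0, Table: Protocol Chart, row for visits 11-24:** "11 and 24 visit: C-SSRS/BDI/BAI".
- **Synopsis, Safety Assessments:** the C-SSRS and the Beck inventories are due at every outpatient visit that the protocol defines, with no exception for the programming visits.

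The length of the block is variable. The synopsis (Study Design) has patients seen "in clinic daily, for 1-2 weeks", and section 3.0 (Phase 2) says "patients will be seen daily for up to two weeks to optimize DBS parameters (visits 11-24". Section 1.0 (Phase 2) allows extra optimization visits if the period is cut short, and names no scales for them.

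After optimization, patients go home on closed-loop stimulation, "with follow-up clinic visits scheduled every 3 weeks". The same scales are listed "for the first recording session that includes a DBS-on condition, (after the initial up to 2 week period of optimizing stimulation parameters") and again for visits 25-31 in both text and chart.

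**The concern.** Text and chart give different schedules for the same visits, and the chart has one check fewer. Both also attach the final check to a visit number, not to the end of optimization, so it disappears if the block ends before visit 24.

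The timing gives this some weight. Stimulation is off throughout Phase 1, so optimization is each patient's first sustained exposure to it. One of the two targets is the cingulate, for which section 1.0 cites earlier use in depression. Under section 7.0, onset of suicidality halts the study for the patient, and two patients meeting any of the halting criteria halt the whole study pending DSMB and FDA review. The C-SSRS is the structured instrument that the synopsis names for suicidality. A schedule that depends on which page staff use is weak support for that rule.

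**Working it through.** There is no sponsor figure to reproduce. The check compares the two lists and counts visits.

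**Inputs.** Visits 11-24, one per day (section 3.0); text list {11, 18, 24}; chart list {11, 24}; 10 patients (synopsis).

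**Full two weeks.** Number of visits = 24 − 11 + 1 = 14. Visit 11 is day 1, visit 18 is day 8 and visit 24 is day 14.

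- Text: 3 checks, with gaps of 8 − 1 = 7 days and 14 − 8 = 6 days.
- Chart: 2 checks, with one gap of 14 − 1 = 13 days.
- Difference: 1 check per patient, so up to 10 across 10 patients.

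**Early finish.** If k daily visits are held, the last is visit 10 + k. The minimum schedule proposed below is the first visit, visits 18 and 24 if held, and the last visit held.

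| k | Last visit | Checks: chart | Checks: text | Checks: proposed | Days from last check to last visit: chart | Same: text |
|---|---|---|---|---|---|---|
| 1 | 11 | 1 | 1 | 1 | 0 | 0 |
| 2-6 | 12-16 | 1 | 1 | 2 | 1-5 | 1-5 |
| 7 | 17 | 1 | 1 | 2 | 6 | 6 |
| 8 | 18 | 1 | 2 | 2 | 7 | 0 |
| 9-13 | 19-23 | 1 | 2 | 3 | 8-12 | 1-5 |
| 14 | 24 | 2 | 3 | 3 | 0 | 0 |

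The rows below k = 7 apply only under the wording that sets no minimum; the Study Design synopsis implies at least one week. At k = 7 neither visit 18 nor visit 24 takes place, and the only check under either list is at visit 11.

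**Time to the next structured check.** Let d be the days from the last optimization visit to the first follow-up visit. The documents do not state d. At k = 7, the interval between questionnaires is 6 + d days under either list. Assuming d lies between 1 and 21 (follow-up is every 3 weeks), this is 7 to 27 days. Had the course run in full, the chart would have put the next check on day 14. After a 7-day course it falls on day 7 + d, which is earlier than day 14 for d = 1 to 6, the same for d = 7 and later for d of 8 or more. An early finish may therefore delay the next check, but need not.

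**Synopsis rule.** Read literally, it requires up to 14 sets over visits 11-24, against 3 in the text and 2 in the chart.

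**The case against.** The best defence is that the synopsis already covers the gap. If the scales are due at every defined outpatient visit, they are due at whichever optimization visit turns out to be last. The heading for visits 11-24 also describes two full weeks of daily visits, and section 1.0 allows further visits if the period is curtailed. This has force: the missing end check is a gap under the two visit-specific lists, not under every reading of the protocol. It does not remove the problem, because three places give three schedules and the two that staff would work from are the weaker ones.

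The second defence is that little is at stake. Patients are in clinic daily; the numbered text adds a full history and examination at these visits; Phase 2 has daily phone calls; the halting rule does not require a C-SSRS score; and the scales return at follow-up. All of this stands. However, neither the examinations nor the calls are stated to include the C-SSRS.

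A reader might infer three stronger things that the documents do not support.

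- **That the text outranks the chart.** Section 3.0 opens the numbered list with "The schedule of events is as follows" and points to the chart with "Also see Table: Protocol chart", but neither phrase ranks one above the other. The text is not a clean master either: it gives Phase 2 as visits 11-31 in one place and 11-34 in another. The reason to restore visit 18 is that it is the safer version.
- **That an early finish always delays the next check, or leaves a gap of a month.** Any such figure depends on the unstated d and on an assumed minimum course length.
- **That the synopsis should simply be cut back to the visit list.** It is the most protective of the three statements, and nothing in the protocol says that it should yield.

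**Conclusion.** The inconsistency is real and lies in current text. Over a full course the chart costs each patient one of three checks and lengthens the longest gap between questionnaires from 7 to 13 days. This assumes one visit per calendar day and all 14 visits held. Under either visit-specific list, a patient who finishes before visit 24 may start at-home closed-loop stimulation without an end-of-optimization check. For a 7-visit course the only check is at visit 11, 6 days before the last optimization visit. Whether the next structured check then comes later than it otherwise would depends on the date of the first follow-up visit, which is not given.

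These are gaps between questionnaires, not between clinical contacts, and no endpoint or analysis changes. The point is minor: a cheap improvement to a safety schedule.

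**What to change.** 1. Add visit 18 to the visits 11-24 row of the Protocol Chart.
2. In both text and chart, require C-SSRS/BDI/BAI at least at the first optimization visit, at visits 18 and 24 if held, and at the last optimization visit actually held, counting any additional visits under section 1.0.
3. Do not weaken the synopsis wording by default. The sponsor should either apply it to visits 11-24 or state expressly that the visit-specific schedule is the minimum for the daily programming visits.

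**Cost.** From the table, the proposed minimum adds 0 or 1 set per patient to the text (for example 3 − 2 = 1 at 9-13 visits) and 0 to 2 to the chart (3 − 1 = 2 at 9-13 visits). If optimization runs past visit 24, the counts are 4 proposed, 3 text and 2 chart, so the same limits hold. Across 10 patients that is at most 10 or 20 sets, all at visits already held. Applying the synopsis rule in full would mean up to 14 sets per patient over visits 11-24, a heavier burden that the sponsor should choose deliberately.
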